## Introduction

This document is a protocol for a human research study. This study is to be conducted according to United States standards of Good Clinical Practice in accordance with applicable Federal regulations and institutional research policies and procedures.

Prostate cancer (PCa) is the third most common cause of cancer related death in the United States and is the most prevalent non-cutaneous cancer [1]. Pelvic lymph node dissection (PLND) following robot-assisted radical prostatectomy (RARP) is an established technique for determining lymph node metastases [2]. The most frequent post-operative complication of PLND is lymphocele formation. Lymphoceles occur as a result of lymph leakage from lymphatic channels that have been cut during dissection. The Principal Investigator (PI) has previously published findings of an occurrence rate of 51% for lymphocele formation with 15.4% from them being clinically symptomatic. The overall frequency of symptomatic lymphocele in patient's that underwent bilateral PLND was equal 6.6% of the evaluated group in this publication [3].

We hypothesize that the incidence of lymphocele's should decrease significantly by attending to careful sealing of these channels using adequate hemostatic tools [3].

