## Study Design

### RESEARCH DESIGN

The study will be a single institution, single arm prospective trial where by 100 patients will be enrolled.

Participants evaluated and scheduled for a PLND during Robotic Assisted Radical Prostatectomy by [name] who have met the study inclusion criteria and who have also given informed consent will be enrolled. Enrolled participants will have their PLND performed using J-Plasma® for dissection and sealing of lymphatic channels. An abdominal-pelvic ultrasound will be completed at a follow-up period ranging from 4-12 weeks post operatively to determine if a lymphocele is present as this is the standard of care within [name] clinical practice for all patients who undergo a PLND during RARP. The occurrence rate of lymphoceles in this trial group of 100 patients will be compared to retrospective data of 100 patients acquired from the IRB approved Urologic Robotic Surgery Outcomes Registry # 237998 using the same inclusion/exclusion criteria as defined for enrollment in this protocol and from other published data to determine if the occurrence rate has been reduced.

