## INCLUSION CRITERIA

Must answer yes to all:

1. Age 18 – 80
2. Primary diagnosis of Prostate Cancer (ICD-10:C61)
3. Prostate Specific Antigen (PSA) level  $\geq$  10ng/mL and/or Gleason Score  $\geq$  7
4. Planned Elective Robotic Assisted Radical Prostatectomy with planned pelvic lymph node dissection.
5. Willing and able to return to clinic for standard of care abdominal ultrasound within 12 weeks post operatively.
6. Able to provide informed consent

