## Resources Available

The research team assigned to the study for screening, consenting and data collection purposes will be the Research Coordinator who is a RN and three data abstractors that work on post-operative RARP patient follow up. Two members are medical assistants with experience of screening and consenting in research as well as clinical experience in urology.

- Justify the feasibility of recruiting the required number of suitable subjects within the agreed recruitment period. [name] clinical practice sees approximately 900 patients a year in consultation for RARP as treatment for prostate cancer. Approximately 11% will be needed for enrollment.
- There is no additional surgical time needed for this study. The approximate surgical time is 90 minutes.

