## Statistical Analysis Plan

### PRIMARY OBJECTIVE ANALYSIS

The primary variable of interest is the incidence of lymphocele formation measured at approximately 8 weeks post-operatively. The incidence of lymphocele formation will be compared between the 100 enrolled “treatment” group and a propensity matched “non-treatment” group that will be established using equal inclusion/exclusion criteria, this retrospective lymphocele data will be retrieved from the Urologic Robotic Surgery Outcomes Registry identified by IRBnet #237998. Additional comparisons of demographic (age, race/ethnicity) and oncological information will be accessed to ensure no differences between the two groups.

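### Must the plan name its propensity covariates, balance rule and control pool before the registry comparison can be trusted?

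*Combined protocol and SAP*

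**What the plan says.** The study is single arm, at one institution, with 100 treated patients and no randomisation. Three parts of the combined protocol and SAP describe the comparator.

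- Statistical Analysis Plan, Primary Objective Analysis: the comparator is a "propensity matched “non-treatment” group that will be established using equal inclusion/exclusion criteria". On comparability it adds: "Additional comparisons of demographic (age, race/ethnicity) and oncological information will be accessed to ensure no differences between the two groups".
- Study Design, Research Design: the treated rate "will be compared to retrospective data of 100 patients acquired from the IRB approved Urologic Robotic Surgery Outcomes Registry # 237998", under the same eligibility criteria, and also with published data. Matching is not mentioned.
- Study Outcome Measures (Endpoints): the registry comparison is repeated. Age, pre-operative Gleason score, pre-operative PSA, the pathology and radiology reports and the clinical notes are listed for collection. Race/ethnicity is not on that list.

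On dissection, Inclusion Criteria item 4 asks for "Planned Elective Robotic Assisted Radical Prostatectomy with planned pelvic lymph node dissection", with nothing on side or extent. The Introduction gives the mechanism ("Lymphoceles occur as a result of lymph leakage from lymphatic channels that have been cut during dissection") and mentions side only when it reports that the symptomatic rate in patients "that underwent bilateral PLND was equal 6.6% of the evaluated group in this publication".

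**The concern.** Without randomisation, crediting a lower lymphocele rate to the device depends largely on how alike the two groups are. The plan names a method for making them alike but leaves most of its working parts open: covariates, ratio, caliper, balance measure, and what happens if balance fails. Comparing groups does not in itself remove differences.

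Two points sharpen the worry. If the 100 registry patients were the whole pool, matching all 100 treated patients 1:1 would use every control and leave group balance exactly as it was. And if lymphoceles come from cut lymphatic channels, the extent of dissection could plausibly drive the outcome, yet no variable for it is defined. An imbalance in such a driver could imitate a device effect or hide one, and choices left open could be made after outcomes are known.

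**Working it through.** **Inputs from the documents.** Historical lymphocele rate 51% (Introduction); 100 treated and 100 registry patients (Research Design). No alpha, sidedness, power or target rate is given, so the figure of 100 per group cannot be reproduced. Everything else below is assumed, including a two-sided 5% test on independent groups.

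**1. Scale of the comparison.** With pooled standard error √(2·p̄(1−p̄)/n) under the null and √[(p₁(1−p₁)+p₂(1−p₂))/n] under the alternative, 100 against 100 has 80% power for a fall from 51% to about 31.6%, a difference of 51 − 31.6 = 19.4 points.

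**2. What an uncorrected imbalance could do.** Assume a normally distributed driver, 0.3 SD apart between groups, in a logistic model with overall rate 51%.

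| Odds ratio per SD | Treated rate, no device effect | Shift | Chance of a claim for the device |
|---|---|---|---|
| 1.5 | 48.1% | 2.9 points | 6.1% |
| 2.0 | 46.3% | 4.7 points | 9.7% |

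Check of the first row: p̄ = (0.51 + 0.481)/2 = 0.4955; null SE = √(2 × 0.4955 × 0.5045/100) = 0.0707; alternative SE also 0.0707; z = (0.029 − 1.96 × 0.0707)/0.0707 = −1.55, which gives about 6.1%. The nominal value is 2.5%. If the imbalance runs the other way, the chance falls to 0.9% or 0.4%. Against step 1, the shifts are 2.9/19.4 = 15% and 4.7/19.4 = 24% of the detectable difference.

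**3. How much of that survives matching.** Simulation: 1,000 runs, 100 treated, true score difference 0.3 SD, greedy 1:1 nearest neighbour without replacement.

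| Eligible pool | Left without caliper (SD) | Left with 0.2 SD caliper (SD) | Pairs with caliper |
|---|---|---|---|
| 100 | 0.30 | 0.003 | 81 |
| 120 | 0.11 | 0.002 | 88 |
| 150 | 0.04 | 0.002 | 93 |
| 200 | 0.02 | 0.001 | 97 |

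The 0.30 in the first row is true by construction: every control is used. Once there is a pool to choose from, matching does most of the work.

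**4. Pool or matched set?** Set side by side, the SAP establishes a matched group from the registry, and Research Design puts 100 registry patients against 100 treated. The reading that makes sense of both is that the 100 are the matched set. Reading them as the pool makes the SAP's matching pointless. Nothing caps extraction at 100, and Resources Available says the practice "clinical practice sees approximately 900 patients a year in consultation for RARP as treatment for prostate cancer". A pool of 200 would be 200/900 = 22% of one year's consultations. The number of eligible registry patients is not given, so this shows plausibility only.

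**5. Would added adjustment help?** In a second simulation (2,000 runs, odds ratio 2.0 per SD, no device effect), a pool of 200 with a caliper gave a bias of −0.1 points both unadjusted and adjusted. A pool of 120 without a caliper gave −1.9 and −0.1. A pool of 100 without a caliper gave −4.5 and +0.2. The large gain belongs to the reading rejected in step 4.

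**6. Would a mandated caliper help?** It would give fewer than 100 pairs on average at every pool size in step 3, which sits badly with a comparator of 100. Power for 51% against 31% is 82.5% at 100 pairs and 73.4% at 80.

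**7. Dissection side.** If 90% of one group and 70% of the other were bilateral, with an odds ratio of 2 to 3, the rate would shift by 3.4 to 5.2 points. Neither the split nor the odds ratio has a source in the documents. The only mention of side is of bilateral dissection, which fits a uniformly bilateral practice just as well.

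**The case for a change.** The strongest case for a change is that two analysts could both follow the SAP faithfully, choose different scores, and obtain different control groups, possibly after seeing registry outcomes. The balance sentence also promises more than it can deliver. If it were carried out as a 5% significance test with 100 per group, a standardised difference of 0.2 would be detected only 29% of the time and one of 0.1 only 10.5% of the time. Naming the covariates would cost little.

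Much of this stands as a description: the covariates, balance measure and consequence are unwritten. It carries less weight as a reason to amend. The candidate covariates are already in view. The SAP names age, race/ethnicity and oncological information. The endpoints section lists age, PSA and Gleason score for analysis, and eligibility itself turns on PSA "10ng/mL and/or Gleason Score". A competent analyst would match on these, report a balance table, and adjust for or discuss what remains. Propensity matching is itself the confounding control, so the plan is not without one. The absence of race/ethnicity from the collection list is a clerical slip, since the SAP says it will be compared.

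The point about side and extent is a fair question to ask of the practice, but it is not evidence of bias. The pathology reports and physician notes to be collected may hold that information. What remains is residual confounding, which limits any comparison with historical controls and which a longer list of covariates would not abolish.

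**Conclusion.** The concern describes the text accurately but does not call for a change. The plan states the method, the source of controls, the common eligibility criteria and the domains to be compared. What it omits is implementation detail that analysts would fill sensibly. The wording in Research Design and the SAP is reconciled by reading the 100 registry patients as the matched set.

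The possible distortion is about 3 to 5 points on a 51% rate, but only if a 0.3 SD imbalance in a driver with odds ratio 1.5 to 2.0 per SD is left wholly uncorrected. Matching from a pool of 150 to 200 leaves about 0.04 to 0.02 SD of it. Extra adjustment gains nothing where caliper matching from a pool of 200 has already balanced the groups. These figures rest on assumed imbalances, odds ratios and pool sizes, a single perfectly known score, and a two-sided 5% test that the documents do not state. The conclusion would weaken if the eligible registry pool were close to 100, or if dissection extent differed materially between the periods. The documents show neither.

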## Potential Risks and Benefits

### POTENTIAL BENEFITS

Lymphocele’s can lead to symptoms and secondary complications such as abdominal pain, leg pain, lower limb edema, constipation, urinary frequency, deep vein thrombosis and infection or sepsis.

The potential benefits of enrollment of this study will be a hypothesized reduction in the incidence of lymphocele formation thus resulting in a decrease of the symptoms associated with such formation.

### POTENTIAL RISKS

Risks associated with robotic radical prostatectomy as discussed and stated by the physician and included in the surgery consent signed by the patient regardless of enrollment in this study include: severe loss of blood, damage to surrounding organs, tissues, vessels, infection / any of which may necessitate a return to surgery, cardiac arrest which may result from the performance of any surgery/ procedure(s), and in some cases, may lead to partial or permanent disability or death. Additional risks may include, but are not limited to: urinary incontinence, erectile dysfunction, rectal/bowel/ureter injury, bladder neck contracture, pulmonary embolism, urine leak, pneumonia, problems related to positioning and endotracheal tube, blood transfusion, embolus from pneumo-peritoneum, unrecognized injuries and lymphocele formation.

JPlasma® has minimal lateral and depth of thermal spread in a variety of tissue types however; possible risks associated with JPlasma® are: unintended surgical site burns due to direct contact with the cutting tip electrode. Inadvertent activation or movement of the cutting tip instrument outside the field of vision may result in injury to the patient or

surgical team. Electrosurgical devices may cause interference with pacemakers or other implants.

#### MITIGATION OF RISKS

Side effects will be monitored during follow-up study visits.

#### PROVISIONS TO PROTECT THE PRIVACY INTEREST OF SUBJECTS

Subjects will be assigned unique identifiers for study-related records. All precautions will be taken to make sure that only authorized individuals will access subject research records. Each member of the Florida Hospital Celebration GRI research team will have access to the securely stored medical charts within [name] practice, also the team has a unique id and password allowing them access to electronic medical records. All research team members are trained to follow Florida Hospital's policy on the protection of patient's health and private information. The collection of sensitive information about subjects will be limited to minimum necessary to achieve the aims of the research, so that no unneeded sensitive information will be collected.

### **Early Withdrawal of Subjects**

#### INVESTIGATOR WITHDRAWAL OF SUBJECTS

Patients that did not receive a pelvic lymph node dissection at the discretion of the surgeon during their robotic radical prostatectomy will be withdrawn from the study.

Patients that do not return for the abdominal ultrasound post operatively as ordered by the physician will be withdrawn from the study.

If a patient is withdrawn from the study they will be notified via telephone call by GRI Research Staff. After 3 failed attempts by phone a certified letter will be mailed to the patient as the final attempt of notification.

All withdrawn participants will be documented in the regulatory binder.

#### SUBJECT REQUEST FOR WITHDRAWAL FROM STUDY

Subjects may voluntarily withdraw consent at any time during the study without penalty. In all cases of withdrawal, the date and the reason for withdrawal are to be documented per site standard operating procedure.

#### DATA COLLECTION AND FOLLOW-UP FOR WITHDRAWN SUBJECTS

Patients who request withdrawal prior to the post-operative abdominal ultrasound will not be included in the final analysis as there would be unsuccessful collection of the data necessary to conclude the study's end point. Patients who request to withdraw after the abdominal ultrasound will have their data maintained in the research database up to the

point of withdrawal. This data will be included in subsequent analysis because keeping these patients in the analysis is essential for study validity.

## Adverse Event Reporting:

### ADVERSE EVENTS

An **adverse event** (AE) is any untoward or unfavorable medical occurrence in a human subject, including any abnormal sign (for example, abnormal physical exam or laboratory finding), symptom, or disease temporally associated with the subject's participation in the research, whether or not considered related to the subject's participation in the research.

Adverse events will be documented as anticipated or unanticipated; minor or serious; and, related or unrelated to study intervention.

**Serious Adverse Event (SAE)**: A Serious Adverse Event is defined as an AE meeting one of the following outcomes:

- Death during the period of protocol defined surveillance
- Life Threatening Event (defined as a participant at immediate risk of death at the time of the event)
- Inpatient hospitalization or prolongation of existing hospitalization during the period of protocol defined surveillance
- Results in a persistent or significant disability/incapacity

All adverse events that do not meet any of the criteria for “**serious**” should be regarded as **minor adverse events**.

*A preexisting condition is one that is present at the start of the study. A preexisting condition will be recorded as an adverse event only if the frequency, intensity, or the character of the condition worsens during the study period.*

Neither the condition, hospitalization, prolonged hospitalization, nor surgery are reported as an adverse event in the following circumstances:

- Hospitalization or prolonged hospitalization for diagnostic or elective surgical procedures for a preexisting condition. Surgery should **not** be reported as an outcome of an adverse event if the purpose of the surgery was elective or diagnostic and the outcome was uneventful.
- Hospitalization or prolonged hospitalization for therapy of the target disease of the study, unless it is a worsening or increase in frequency of hospital admissions as judged by the clinical investigator.

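### The serious-event definition has no limb for injuries needing intervention, so an operative injury repaired without lasting consequence or a longer stay is labelled minor

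*Combined protocol and SAP*

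**What the plan says.** The Adverse Events section (under Adverse Event Reporting) sets out a closed list: "A Serious Adverse Event is defined as an AE meeting one of the following outcomes". Four outcomes follow:

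- "Death during the period of protocol defined surveillance";
- a life-threatening event, limited to immediate risk of death when it occurs;
- "Inpatient hospitalization or prolongation of existing hospitalization during the period of protocol defined surveillance";
- lasting or significant disability or incapacity.

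Every event outside the list "should be regarded as minor adverse events". The same section also has each event classed by whether it was anticipated and whether it was related to the intervention. It has no severity grade and no class between minor and serious.

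Potential Risks has two lists. The first gives risks of the prostatectomy that apply whether or not the patient enrols. It includes "damage to surrounding organs, tissues, vessels, infection / any of which may necessitate a return to surgery", and also rectal, bowel and ureter injury. The second gives risks of the device: surgical site burns from contact with the electrode, interference with implants, and the warning that "Inadvertent activation or movement of the cutting tip instrument outside the field of vision may result in injury to the patient" or the surgical team.

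**The concern.** The protocol recognises that some operative injuries are important because they need further surgery, but its definition of seriousness does not use that criterion. The device is used only on the day of surgery (Study Visits), so an injury it causes would arise in the operating room and could be repaired there. If the repair succeeds and discharge is on time, the event falls into the same class as a trivial complaint.

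What is at stake is the safety statement. The device's rationale rests on limited thermal injury to neighbouring tissue (Background Information and Scientific Rationale). A report of no serious adverse events would be read as support for that, yet under this definition it could be literally true even if organs had been injured and repaired. The word minor makes this worse, because it describes severity while the rule only establishes that four outcomes were absent.

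**Working it through.** No figure in the plan bears on this point and no arithmetic applies. The check sets the definition in Adverse Events against the harms in Potential Risks, one limb at a time.

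**Events that meet no limb.** Assume no immediate risk of death, no longer stay or readmission, and no lasting or significant disability.

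| Event | Death | Immediate risk of death | Admission or longer stay | Lasting or significant disability | Class |
|---|---|---|---|---|---|
| Electrode burn treated during the operation | no | no | no | no | minor |
| Rectal, bowel or ureter injury repaired in the same operation | no | no | no | no | minor |
| Vessel or other organ injury repaired in the same operation | no | no | no | no | minor |
| Later drainage or other re-intervention without admission | no | no | no | no | minor |

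**Events the definition does catch.** Change one assumption and the class changes. A vessel injury with immediate risk of death is serious under the second limb. An injury that leads to readmission or a longer stay is serious under the third. One that leaves lasting or significant disability is serious under the fourth. The gap is therefore narrower than all repaired injuries.

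**How the hospitalization limb works here.** Participants are already in hospital for planned surgery. For an injury in the operating room, this limb can act only through a longer stay or a readmission. The repair itself does not trigger it.

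**Search for a rule elsewhere that raises such events to serious.**

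- The closing exclusions in Adverse Events remove some hospitalizations and elective surgery from reporting. They raise nothing to serious.
- Recording and Notification of Adverse Events sends all events to the source record, the case report form and the IRB under local guidelines. It adds no seriousness criterion.
- Mitigation of Risks says only that side effects will be monitored at follow-up visits.
- The Safety Monitoring Plan has the principal investigator review the data with the research coordinator, every 25 subjects or every 4 months, whichever comes first. There is no data and safety monitoring board. No reclassification step is described.
- Study Outcome Measures and the Statistical Analysis Plan concern lymphocele and baseline comparisons. Neither includes a safety analysis that would group these injuries in another way.

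Nothing corrects the label.

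**The case against.** The strongest reply is that nothing in the documents turns on the label. Minor and serious events alike are recorded promptly, classed for relatedness and expectedness, and reported. The investigator's review is triggered by enrolment or elapsed time, not by serious events, and no stopping rule or expedited step is tied to the word. The IRB guidelines are not reproduced and may apply their own classification. All of this stands. It confines the point to how events are classed and later described.

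Several stronger readings are tempting, and the documents do not support them:

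- *Injuries would go unrecorded.* They would not; capture and reporting cover every event.
- *The study would publish too low a serious-event rate or confidence limit.* No such rate or interval is planned and no injury rate is given, so any numerical contrast would rest on an invented count.
- *Organ, bowel and ureter injuries are stated device harms.* Potential Risks lists them as risks of the operation. The device list is burns, injury from inadvertent activation or movement, and interference with implants. A device injury could reach an organ, but the protocol does not say so.
- *Thrombosis and infection as listed under Potential Benefits show the same gap.* That passage lists consequences of lymphocele, so it is not evidence about intra-operative injury.
- *Any injury repaired without a longer stay is minor.* This holds only if the life-threatening and disability limbs are also unmet.

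It can also be said that a limb covering any treated complication would make an infection given antibiotics serious, so that the class no longer discriminates. That is correct, and it is why the added limb has to be narrow.

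**Conclusion.** The point holds as a defect of classification and should be corrected. A stated rule places in the minor class a set of injuries that the protocol itself names as important risks, and no severity grade separates them from trivial events. The consequence is that the study could report no serious adverse events although injuries needing repair had occurred.

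The size cannot be quantified from the documents. The conclusion rests on reading the four outcomes as exhaustive, which the residual sentence requires. It also assumes that injuries repaired without meeting any of the four can occur; the documents do not say how often. The lymphocele comparison is unaffected.

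**What to change.** In Adverse Events, add a fifth serious outcome: *an event that required unplanned surgical or procedural intervention (including intra-operative repair of an unintended injury, return to surgery or percutaneous drainage) to prevent permanent impairment or damage*. In the residual sentence and in the classification list, replace minor with *non-serious*, so that the term claims no more than the rule establishes.

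The closing condition on permanent impairment or damage should stay, because it keeps routinely treated complications out of the serious class. No separate device-relatedness field is needed: relatedness to the intervention is already recorded, and Study Visits describes the device as the only item outside standard care.

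The change is one added line and one replaced word, carried through to the adverse event module of the case report form. It adds no visit, procedure or participants. The downside is that a few more events will be classed and reported as serious. It should be made before events are coded, since later reclassification would be post hoc.
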